7.3.2. Discontinuation of Study Sites

Study site participation may be discontinued if Lilly, the investigator, or the ethical review board (ERB) of the study site judges it necessary for medical, safety, regulatory, ethical, or other reasons consistent with applicable laws, regulations, and Good Clinical Practice (GCP).

7.3.3. Discontinuation of the Study

The study will be discontinued if Lilly judges it necessary for medical, safety, regulatory, ethical, or other reasons consistent with applicable laws, regulations, and GCP.

8. Investigational Plan

8.1. Summary of Study Design

Study JBAL is a 3-arm, randomized, multicenter, global, Phase 2 study of LY2157299 monotherapy or LY2157299 plus lomustine therapy compared to lomustine plus LY2157299-matched placebo therapy in patients with relapsed or progressed GB. **CCI**

■ patients will be entered with the aim of randomizing **CCI** patients in a **CCI** fashion to LY2157299 monotherapy or LY2157299 plus lomustine therapy or lomustine plus LY2157299-matched placebo therapy (see Section 12.1). **Figure JBAL.8.1** illustrates the study design. Patients and investigators will be blinded to the LY2157299 or placebo assignment for those patients who receive lomustine. One cycle is defined as 28 days in all treatment arms and constitutes 14 days on/14 days off of LY2157299/LY2157299-matched placebo.

Figure JBAL.8.2 illustrates an overview of the first 4 cycles for each treatment arm.

[figure not shown]

Figure JBAL.8.1. Illustration of study design for Protocol H9H-MC-JBAL.

[figure not shown]

Figure JBAL.8.2. Illustration of LY2157299 and lomustine administration for the first 4 treatment cycles in Protocol H9H-MC-JBAL.

In Cycle 1, lomustine will be given after LY2157299 or placebo has been given for 7 days (on Day 7 of Cycle 1). After the first dose, lomustine will then be given once every 6 weeks to those patients assigned to either the LY2157299 plus lomustine or lomustine plus placebo treatment groups. The planned treatment with lomustine will be limited to 6 administrations. For details, see Section 9.1.

[figure not shown]
The primary comparison for efficacy is to compare OS between the LY2157299 plus lomustine therapy and lomustine plus placebo therapy. Additional endpoints (eg, PFS, response rate) will be estimated.

Further analyses will be carried out to estimate efficacy and safety endpoints for LY2157299 monotherapy and LY2157299 plus lomustine therapy. This secondary analysis will provide an assessment of whether the monotherapy treatment with LY2157299 is as active as lomustine alone. At the same time, this design will offer additional information whether LY2157299 monotherapy has a toxicity profile that warrants further investigation.

8.1.1. Baseline and Study Treatment Period Assessments

Terms used to describe the study baseline and treatment periods are defined below:

- **Baseline:** After signing Informed Consent and from the time of screening to first study treatment (or discontinuation, if no treatment is given)
- **Study Treatment Period:** Time from treatment start to discontinuation from study treatment (does not include the continued access period)

The Study Schedule ([Attachment 1](#)) describes the timing of baseline and study treatment period assessments.

Written informed consent must be obtained prior to any study-specific pretreatment evaluations. At baseline, within 28 days prior to dosing, and during the study treatment period, medical and physical examinations, ECOG PS evaluation, health outcome assessments (Section [10.2](#)), ECG/ECG chemistry (Section [10.3.2.1](#)), ECHO/Doppler and chest CT scans (Section [10.3.2.2](#)), pregnancy test (as applicable), serum chemistry, urinalysis and hematology laboratory tests (Section [10.4.1](#)) in addition to tumor measurements by MRI will be completed. In addition, pulmonary function tests will be conducted on those patients receiving lomustine at baseline and every 6 months thereafter (Section [10.3.2.3](#)).

Tumor measurements will be performed by MRI every 2 cycles until objective progression is observed, per efficacy measurement criteria described in Section [10.1.1](#). Tumor responses will be confirmed. Imaging methods used at baseline must be consistently used during study.

All enrolled patients will be assessed for toxicity before each cycle using CTCAE, version 4.0. Trial-level safety monitoring will be done as specified in [Table JBAL.10.3](#) (Section [10.3](#)).

Pharmacokinetic sampling (Section [10.4.4](#)) will be conducted during Cycle 1. Additionally, samples will be collected for biomarker, PD, and patient tailoring research (Section [10.4.3](#)).

Cerebrospinal fluid (CSF) may be collected by lumbar puncture.

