Bevacizumab 10 mg/kg + Irinotecan 340/125 mg/m ² (48)	17% (35)	-	31 wks (21-54)	16 wks (12-26)	29% (18-48)	(Kreisl et al. 2009)
Bevacizumab 10 mg/kg (84)	28.2% (18.5-40.3)	-	9.2 mo (8.2-10.7)	4.2 mo (2.9-5.8)	42.6% (29.6-55.5)	(Friedman et al. 2009)
+ Irinotecan 340/125 mg/m ² (82)	37.8% (26.5-50.8)	-	8.7 mo (7.8-10.9)	5.6 mo (4.4-6.2)	50.3% (36.8-63.9)	
Meta-analysis of 15 studies (548)	55% (2-61)	29% (20-38)	9.3 mo (7.9-10.6)	6.1 mo (4.2-8.1)	45% (34-57)	(Wong et al. 2011)
Enzastaurin						
Enzastaurin (174)	3% 4.14-9.63	38%	6.6 mo (5.2-7.7)	1.5 mo (1.45-2.10)	-	(Wick et al. 2010a)
Lomustine (92)	4% 2.79-9.62	36%	7.1 mo (6.0-8.8)	1.64 mo (1.48-2.79)	-	
Cediranib (2:2:1)						
Cediranib (30 mg/day) (131)	-	-	8 mo	92 days	16%	Batchelor et al. 2010a
Cediranib (30 mg/day) + lomustine 110 mg/m ² (129)	-	-	9.4 mo	125 days	34%	
Placebo + lomustine 110 mg/m ² (129)	-	-	9.8 mo	82 days	24%	

Abbreviations: CI = confidence interval; mo = months; ORR = overall response rate; OS = overall survival; PFS = progression-free survival; SD = stable disease; wks = weeks.

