9.4.1.3. LY2157299 Dose Adjustments and Delays

At the time of writing this protocol, no specific toxicities for LY2157299 have been identified in patients. Hence, the investigator is asked to contact the Lilly physician if there is a drug-related toxicity which is attributed to LY2157299.

While no bone marrow toxicities were detected in nonclinical toxicology studies, there was 1 case in a patient with GB in which a Grade 4 thrombocytopenia was observed and potentially

associated with administration of LY2157299 monotherapy. In similar cases, the drug should be discontinued until thrombocyte counts either return to Grade 1 or baseline.

Subsequent courses of LY2157299/placebo will be adjusted for any patient who experiences unacceptable toxicity based on nadir counts, maximal nonhematologic toxicities, or other severe events which are related to LY2157299 or its combination with lomustine. This decision will be made in the context of the known safety profile of lomustine monotherapy.

The first dose reduction of LY2157299 should be to approximately **CCI** mg/day and no re-escalation should be performed unless there is clinical benefit expected in the opinion of the investigator.

A further 50% dose reduction should only be considered in rare circumstances.

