10.1.2. Efficacy Assessments during the Postdiscontinuation Period

After patients have discontinued study treatment, they may receive additional anticancer therapy at the discretion of the investigator.

For those patients who discontinue study treatment without objectively measured progressive disease, the investigative sites will continue to monitor patients approximately every 60 days (± 14 days) to evaluate tumor response by the same method used at baseline and throughout the study, until objective progression or the patient starts a new anticancer therapy.

Once a patient has objective progression or starts a new anticancer therapy, they will be followed for OS approximately every 60 days (± 14 days) until death or study completion.

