10.1.4. Secondary Efficacy Endpoints

The secondary time-to-event endpoints are defined in [Table JBAL.10.1](#).

Table JBAL.10.1. Secondary Efficacy Endpoints

Endpoint	Definition
Progression-Free Survival	The time from the date of study enrollment (randomization) to the date of first observation of objective progression or death from any cause, whichever occurs first. For patients who are not known to have died or progressed as of the data-inclusion cut-off date, PFS time will be censored at the date of the last objective progression-free disease assessment prior to the date of any subsequent systematic anticancer therapy.
Progression-Free Survival at 6 months	Number of patients not having objective progression or death at 6 months after the time from date of study enrollment (randomization) estimated from the PFS distribution.
Survival at 12 months	Number of patients alive 12 months after start of treatment, even if they have progressed, estimated from the overall survival distribution

Abbreviation: PFS = progression-free survival.

The use of MRI is mandatory to determine tumor response and to assess when objective progressive disease has occurred (for use in estimating PFS). Recent guidelines have modified the MacDonald criteria and these new guidelines are attached in [Attachment 5](#) and are referred to as the RANO criteria (Wen et al. 2010). The MRI scans will be collected and stored centrally; if necessary, independent review of all or a representative sample of scans may be considered following study completion.

Overall response rate (ORR) is the proportion of patients who achieved a complete response (CR) or partial response (PR) out of all randomly assigned patients.

Based on RANO criteria, a responder is defined by radiographic and clinical criteria (see [Attachment 5](#)). Complete response or PR will be first assessed by radiographic changes as determined by an improvement of the bi-dimensional evaluation of the tumor size. In addition, changes in neurologic function and steroid use will be considered to determine stable disease (SD).

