5.1. Summary of Study Design

Study JBAL is a 3-arm, randomized, multicenter, global, Phase 2 study of LY2157299 monotherapy or LY2157299 plus lomustine therapy compared to lomustine plus LY2152799-matched placebo therapy in patients with relapsed or progressed GB.

CCI [REDACTED] patients will be entered with the aim of randomizing CCI [REDACTED] patients in a CCI [REDACTED] fashion to LY2157299 monotherapy or LY2157299 plus lomustine therapy or lomustine plus LY2152799-matched placebo therapy. Patients and investigators will be blinded to the LY2157299 or placebo assignment for those patients who receive lomustine. One cycle is defined as 28 days in all treatment arms and constitutes 14 days on/14 days off of LY2157299/LY2157299-matched placebo.

[figure not shown]
In Cycle 1, lomustine will be given after LY2157299 or placebo has been given for 7 days (on Day 7 of Cycle 1). After the first dose, lomustine will then be given once every 6 weeks to those patients assigned to either the LY2157299 plus lomustine or lomustine plus placebo treatment groups. The planned treatment with lomustine will be limited to 6 administrations.

Patients will receive treatment until disease progression, death, or discontinuation occurs. Patients will be followed for OS until death or study closure. Tumor assessments will be conducted at baseline (within 28 days before the first dose of study drug or 14 days prior to enrollment) and at the end of every 2 cycles (Day 26 ± 2) thereafter.

The primary comparison for efficacy is to compare OS between the LY2157299 plus lomustine therapy and lomustine plus placebo therapy. Additional endpoints (eg, PFS, response rate) will be estimated.

Further analyses will be carried out to estimate efficacy and safety endpoints for LY2157299 monotherapy and LY2157299 plus lomustine therapy. This secondary analysis will provide an assessment of whether the monotherapy treatment with LY2157299 is as active as lomustine alone. At the same time, this design will offer additional information whether LY2157299 monotherapy has a toxicity profile that warrants further investigation.

CCI [REDACTED] interim assessments are planned:

The planned duration of the study is CCI [REDACTED] in order to follow all patients for OS. Overall survival will be collected for all patients, including those who started other

therapies after discontinuation from study drug treatment.

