Study day	If assessment is on or after date of first LY2157299/ LY2152799-matched placebo dose then (date of assessment) – (date of first study treatment dose) + 1 If assessment precedes first treatment dose then (date of assessment) – (date of first study treatment dose)

	There is no study day 0. Study day 1 is the date of first dose and study day -1 is the day before the first dose.
Cycle day	If assessment is on or after date of first LY2157299/ LY2152799-matched placebo dose then (date of assessment) – (date of first study treatment dose in cycle) + 1 If assessment precedes first treatment dose then (date of assessment) – (date of first study treatment dose in cycle) There is no cycle day 0. Cycle day 1 is the date of first dose in the cycle and cycle day -1 is the day before the first dose.
Baseline	For change from baseline analysis, baseline value is defined as the last reported measure on or before the first dose date (or discontinuation, if no treatment is given). For change from baseline within a cycle, the measure prior to the first dose if that cycle is baseline.
Study treatment period	Time from treatment start to discontinuation from study treatment
Post-discontinuation – short-term follow-up	The short term follow-up period begins 1 day after discontinuation of study treatment and lasts approximately 30 days (Visit 801).
Post-discontinuation – long-term follow-up	The long-term follow-up period begins 1 day after the short-term follow-up period (Visit 801) is completed and continues until death to collect survival data.

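### On-treatment MRI follows treatment cycles, not the calendar, so cycle delays that differ by arm can bias the secondary PFS comparisons, mainly monotherapy against the lomustine arms

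*Protocol*

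**What the plan says.** On treatment, Protocol 8.1.1 sets the interval in cycles: "Tumor measurements will be performed by MRI every 2 cycles until objective progression is observed". Protocol 10.1.1 likewise repeats the assessment every other cycle. Protocol 8.1 adds that "One cycle is defined as 28 days in all treatment arms", and SAP 5.1 puts the scan "at the end of every 2 cycles (Day 26 ± 2) thereafter". The SAP's data definitions (Table JBAL.6.1) count cycle day from the "date of first study treatment dose in cycle".

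PFS runs from randomization "to the date of first observation of objective progression or death from any cause" (Protocol 10.1.4; SAP 6.10 agrees). PFS hazard ratios between all three arms are planned from proportional hazards models (SAP 6.10.3). The only related sensitivity analysis is an optional change of censoring dates (SAP 6.10.4).

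On delays, Protocol 9.4.1.3, whose title covers both adjustments and delays, says "Subsequent courses of LY2157299/placebo will be adjusted for any patient who experiences unacceptable toxicity based on nadir counts". Delays are to be tabulated (Protocol 12.2.5 and 12.2.10), but no expected rate is given for any arm.

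After treatment stops without progression, a different clock applies: sites "monitor patients approximately every 60 days" (Protocol 10.1.2), with a window of ± 14 days.

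**The concern.** A patient whose Cycle 2 starts a week late has the first scan a week late, if the scan follows the cycle. A progression already present is then recorded a week later. When this happens equally in all arms it blurs PFS but does not bias the comparison. When it happens more in one arm, that arm looks better.

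The protocol gives a reason to expect inequality. Section 8.2 contrasts the favourable toxicity profile of LY2157299 with the well-known marrow toxicity of lomustine, and only two of the three arms receive lomustine. Section 8.1 says the secondary analysis will judge whether monotherapy is as active as lomustine alone. If the lomustine arms are delayed more, the artefact works against monotherapy in that comparison.

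**Working it through.** The plan states no PFS design figure (expected median, hazard ratio, events or power), so there is none to reproduce.

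**Scan calendar.** First scan = 28 + 26 = Day 54 (52 to 56) from first dose, then every 56 days: Days 110, 166, 222.

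**Reference medians.** Table JBAL.5.1 has two lomustine control arms. The enzastaurin trial gives "1.64 mo (1.48-2.79" as median PFS with its 95% limits. In days, 1.64 × 30.4375 = 49.9, with limits of 45 and 85. The cediranib trial gives 82 days. Under an exponential curve, the share progressed by Day 54 is 1 − 2^(−54/median):
- median 49.9 days: 1 − 2^(−54/49.9) = 53%
- median 82 days: 1 − 2^(−54/82) = 37%

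Day 54 therefore lies between the two references.

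**Which delays move the scan.** In Attachment 1 the second lomustine dose is Cycle 2 Day 21, that is Day 28 + 21 = 49. Holding that dose alone does not move the Day 54 scan. A late Cycle 2 start of LY2157299/placebo can. That start is planned for Day 29, which is 29 − 7 = 22 days after the first lomustine dose and inside the six-week recovery period described in Protocol 9.4.1.1.

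**Simulation with no true difference.** Both arms have the same exponential PFS, with total hazard ln 2/median. Deaths are split out at an 8.5-month median OS and dated exactly. Scans fall on Day 26 ± 2 of every second cycle, and progression is dated at the next scan. Each new cycle in one arm starts 7 or 14 days late with the stated probability. There are 200,000 patients per arm. The Cox hazard ratio is more delayed over less delayed arm. Delay rates, delay lengths and the 30% clinical-detection share are assumptions.

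| Cycles delayed (other arm) | Days late | Median 49.9 d, scans only | Median 49.9 d, 30% found clinically | Median 82 d, scans only | Median 82 d, 30% found clinically |
|---|---|---|---|---|---|
| 0% (0%) | – | 1.00 | 1.00 | 1.00 | 1.00 |
| 30% (10%) | 7 | 0.93–0.94 | 0.96 | 0.98 | 0.98 |
| 30% (0%) | 7 | 0.92 | 0.96 | 0.96 | 0.98 |
| 50% (0%) | 7 | 0.89 | 0.93 | 0.95 | 0.97 |
| 100% (0%) | 7 | 0.85 | 0.90 | 0.93 | 0.95 |
| 100% (0%) | 14 | 0.84 | 0.89 | 0.93 | 0.95 |

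A repeat run under the same assumptions agreed to about 0.01.

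At a 49.9-day median with scans only, 30% of cycles delayed 7 days moves the observed median from 56 to 62 days. The one-sided 10% log-rank error rises to 0.21–0.24, with assumed arm sizes of 40 v 40 and 80 v 40 because the true sizes are redacted. With every cycle 7 days late, six-month PFS reads 14% against 10% (49.9-day median) or 29% against 23% (82-day median).

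**A second delay model.** Here a fraction of patients is delayed once, by 7 or 14 days, before the first scan, and the other arm is never delayed. With progression found only at scans and a 49.9-day median, the hazard ratio is 0.91–0.93 (25% delayed) and 0.84–0.87 (50% delayed). With an 82-day median it is 0.95–0.96 and 0.90–0.92. Counting deaths and 30% clinical detection, it is 0.96–1.00 (25%) and 0.93–0.96 (50%) across both medians.

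**After the fix.** Identical scan dates in both arms return the hazard ratio to 1.00.

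**The case against.** **The mechanism is not spelled out.** A cycle is defined as 28 days in every arm, and 10 to 14 dosing days count as compliant, so missed doses could be omissions inside a fixed cycle. The cycle-day entry in the SAP is a data-handling definition, not a scheduling rule. The nadir-count sentence speaks of adjustment, and the text after it concerns dose reduction. The platelet hold in Protocol 9.4.1.3 comes from one case on monotherapy, so it does not show that delays concentrate in the lomustine arms. This stands as a reason to state the point conditionally. It does not supply a calendar anchor, and under the SAP definition a late first dose does shift Day 26.

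**The first scan is not shown to be late.** A reader might infer that it comes after the expected median PFS. The documents give no expected median, and Day 54 exceeds only one of the two lomustine references.

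**The effect is limited.** Deaths and RANO clinical deterioration count as events between scans and pull the hazard ratio towards 1. In some scenarios a 14-day delay biases less than a 7-day delay, so part of the effect is how scan dates interleave. PFS is secondary and estimated. The blinded pair shares lomustine, and Protocol 5.7 reports no added toxicity for the combination. All of this stands.

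**The operative rule may be hidden.** Protocol 8.1 refers scan timing to Attachment 1, whose grid marks tumour assessment in Cycles 2 to 12 and whose comments are redacted. This also stands.

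**Conclusion.** The concern holds as a conditional one. Visible text ties on-treatment scans to cycles and dates progression at observation, and no planned analysis corrects for unequal scan timing. If late LY2157299/placebo cycle starts move scans and differ by arm, PFS can favour the more delayed arm with no drug effect.

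It would go too far to conclude that delays will change the PFS result: their frequency by arm is unknown, and a held lomustine dose alone does not move the first scan. On the assumptions above, the likely distortion is modest, with a hazard ratio of roughly 0.9 to 1.0. Values of about 0.84 to 0.87 need frequent delay in one arm only and progression found only at scans. The OS conclusion is untouched. This is a cheap improvement to a secondary endpoint, not a flaw in the primary analysis.

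**What to change.** First check the redacted Attachment 1 comments for a rule that already fixes scan dates.

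If there is none:
- In Protocol 8.1.1, 10.1.1 and Attachment 1, and in SAP 5.1, schedule MRI every 8 weeks from randomization in all arms, regardless of dose holds, delays or cycle number, with a window no wider than needed.
- In Protocol 10.1.2, replace the 60-day interval with the same calendar until progression or new anticancer therapy.
- In SAP 6.10.4, add an interval-censored PFS sensitivity analysis.

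The cost is mostly wording. The number of scans is essentially unchanged (56 days against two 28-day cycles). In a delayed patient an MRI may not coincide with a cycle visit. The change removes the between-arm timing artefact but not the coarse spacing: with a true median of 82 days, the simulated observed median is still about 109 days.

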8.1.2. Postdiscontinuation Follow-Up Period Assessments

Terms used to describe the postdiscontinuation of study treatment are defined below:

- **Postdiscontinuation Follow-Up:** Begins the day after the patient and the investigator agree that the patient will no longer continue study treatment.
 - **The short-term follow-up period** begins 1 day after discontinuation of study treatment and lasts approximately 30 days (Visit 801).
 - **The long-term follow-up period** begins 1 day after the short-term follow-up period (Visit 801) is completed and continues until death or study completion to collect survival data.

The Study Schedule ([Attachment 1](#)) describes all assessments for the post discontinuation and follow up periods. All patients should be followed and all AEs (Section [10.3](#)) reported for a minimum of 30 days from the date of discontinuation or until completion of Visit 801.

At Visit 801, physical examinations, ECOG PS evaluation, health outcome assessments (Section [10.2](#)), ECG/ECG chemistry (Section [10.3.2.1](#)), ECHO/Doppler (Section [10.3.2.2](#)), serum chemistry, urinalysis, and hematology laboratory tests (Section [10.4.1](#)) will be completed. Additionally, after Visit 801, ECG/ECG chemistry and ECHO/Doppler will be performed as indicated in Section [10.3.2.1](#) and Section [10.3.2.2](#), respectively.

After discontinuation, tumor measurements will be performed as indicated in Section [10.1.2](#).

